9.1 Adverse Events Definitions

Adverse Events:

Any untoward medical occurrence, unintended disease or injury, or untoward clinical signs (including laboratory findings) in subjects, users or other persons, whether or not related to the medical device.

Adverse Device Effects:

An adverse event related to the use of a medical device.

Device Deficiency:

An inadequacy of a medical device with respect to its identity, quality, durability, reliability, safety or performance. Device deficiencies include malfunctions, user errors and inadequate labelling.

Collection of Adverse Events:

Adverse events will be collected for randomized subjects only.

Serious Adverse Events (SAE):

An adverse event that:

- Led to death;
- Led to a serious deterioration in the health of a subject, that resulted in 1) a life threatening illness or injury, or 2) a permanent impairment of a body structure or a body function, or 3) in patient or prolonged hospitalisation or 4) medical or surgical intervention to prevent life threatening illness or injury or permanent impairment to a body structure or a body function
- Led to foetal distress, foetal death or a congenital abnormality or birth defect

Unanticipated Adverse Device Effects (UADE):

Any serious adverse effect on health or safety or any life-threatening problem or death caused by, or associated with, a device, if that effect, problem or death was not previously identified in nature, severity, or degree of incidence in the investigational plan or application (including a supplementary plan or application), or any other unanticipated serious problem associated with a device that relates to the rights, safety, or welfare of subjects.

9.2 Anticipated Adverse Events

There are a number of known potential adverse events that have been documented, or are theoretically potential adverse events with Neuromuscular Electrical Stimulation (NMES).

Potential anticipated adverse events inherent to the use of Neuromuscular Electrical Stimulation (NMES) including:

- Temporary skin reaction (irritation, redness and/or inflammation) at or near the stimulation site during and following periods of stimulation;
- Discomfort and pain (including throbbing pain) at or near the stimulation site;
- Stomach ache;

- Change in bowel habits;
- Twitching, numbness, muscular contraction, tightening, aching;
- Use of excessive intensity or usage time can cause muscle injury;
- On very rare occasions, some patients have reported feeling light-headed or faint, so it is recommended that patients have somewhere to sit nearby should this happen.

Potential anticipated adverse events specifically related to the use of the Neurotech Vital Compact device:

- Develop a sensitivity to the hydrogel electrodes

Potential anticipated adverse events specifically related to the use of the iTouch Sure Pelvic Floor Exerciser:

- Abdominal cramps
- Vaginal irritation or infection.

9.4 Institutional Review Board (IRB) Reporting

All serious adverse events, unanticipated adverse device effects and/or device deficiencies will be reported to the Institutional Review Board in accordance with the local site requirements and to Bio-Medical Research Ltd in accordance with the Study Specific Procedure for the study.

9.5 Food and Drug Administration (FDA) Reporting

This study is considered a Nonsignificant Risk Device Study and is being conducted in accordance with the abbreviated Investigational Device Exemption (IDE) requirements set forth in 21 CFR 812.2(b).

All necessary reporting to the FDA as outlined in FDA guidance (Records under 812.140(b) 4 and 5 and Reports under 812.150(b) 1-3 and 5-10) will be followed.

10 Statistical Analysis

This section describes the statistical methods to be used for the analysis and reporting of data collected under BMR-13-1001. Additional details will be provided in the statistical analysis plan (SAP).

10.1 Analysis Populations

The primary analysis population will be the intent to treat (ITT) population. This will include all randomized subjects. Patients will be summarized according to their randomized assignment.

A per-protocol (PP) population will also be evaluated for the primary endpoint. The PP population will consist of the following subjects and may be further defined in the Statistical Analysis Plan (SAP):

- Signed informed consent
- Meet inclusion/exclusion criteria
- Treated per randomized assignment
- 12 week outcome data available

The Safety population will include all randomized subjects who used the device at least once. Patients will be summarized according to the actual device used, rather than the randomized assignment.

10.2 Sample Size

Sample size calculations were performed using the NQuery Advisor® version 5.0, under a two group test of proportions.

Research suggests that the response rates for Neurotech Vital and itouch Sure at 12 weeks will be 71% and 46%, respectively (itouch success rate based on Sand, 1995).

The sample size calculation is based on the assumption that the itouch Sure Pelvic Floor Exerciser success rate is 52% and the Neurotech Vital Control success rate is 71%. A sample size of 87 subjects per group will provide 90% power using a one-sided Type I error rate of 0.025, and a non-inferiority margin of 5%. A randomization allocation of 1:1 was also assumed. For practical reasons, the sample size has been increased to a recruitment of 180 patients (90 patients per treatment group).

10.3 Statistical Methods

10.3.1 General Statistical Considerations

Data will be summarized using descriptive statistics. For continuous measures this will include mean, standard deviation, median, and range. For categorical measures, counts and percentages will be provided. Data will be summarized separately for each randomized arm under the principles of intent to treat, unless otherwise noted.

10.3.2 Primary Endpoint

The primary endpoint is defined as the proportion of subjects considered to have achieved 'significant improvement' following a provocative pad weight test at 12 weeks compared to baseline.

'Significant improvement' is defined as a greater than 50% reduction in pad weight from baseline.

10.3.3 Hypothesis test

The primary hypothesis that will be tested is that the proportion of patients who respond (i.e. have achieved 'significant improvement') using Neurotech Vital Compact is not less than 5% worse than the itouch Sure Pelvic Floor Exerciser (i.e. the lower bound of the confidence interval about the difference between device groups should be greater than - 5%).

Using a one-sided 2.5% level significance test:

$$H_0: p_{\text{Neurotech Vital Compact}} - p_{\text{CONTROL}} \leq -5\%$$

$$H_1: p_{\text{Neurotech Vital Compact}} - p_{\text{CONTROL}} > -5\%$$

Where $p_{\text{Neurotech Vital}}$ is the proportion of patients who respond on receiving Neurotech Vital Compact and similarly p_{CONTROL} for the itouch Sure Pelvic Floor Exerciser.

If the primary non-inferiority endpoint is met, a hierarchically nested test of superiority will be performed. The hypothesis test for the assessment of superiority is as follows, using a one-sided 2.5% level significance test:

$$H_0: p_{\text{Neurotech Vital Compact}} - p_{\text{CONTROL}} \leq 0\%$$

$$H_1: p_{\text{Neurotech Vital Compact}} - p_{\text{CONTROL}} > 0\%$$

Where $p_{\text{Neurotech Vital}}$ is the proportion of patients who respond on receiving Neurotech Vital Compact and similarly p_{CONTROL} for the itouch Sure Pelvic Floor Exerciser.

10.3.4 Analysis Methods

For the primary analysis variable (proportion of patients who respond at Week 12) the difference in the proportions of responders and a 95% CI of the difference in proportion of responders will be calculated using the normal approximation to the binomial distribution. The ITT population will serve as the primary analysis population, with PP population analyses serving as supportive. For the ITT analysis, if a subject does not complete the 12 week assessment, their outcome will be imputed using multiple imputations. Non-inferiority will be claimed if the lower limit of the 95% CI is greater than -5%.

The total number of successes in each study arm will be summarized, along with the corresponding proportions and 95% CIs. The difference between proportions will also be summarized with its corresponding 95% CI.

Sensitivity analyses will be performed to assess the impact of missing data on the primary endpoint results. These analyses will be based on the ITT population. A last observation

carried forward (LOCF) method will be used to account for all missing data. A tipping point analysis will also be performed (Campbell et al., 2011 and Yan X. et al., 2009).

10.3.5 Key Secondary Endpoints

The key secondary endpoints listed below will be tested only if the primary efficacy endpoint is met. These endpoints will each be tested at a 5% two-sided significance level. In order to control the type I error rate the endpoints will be analysed in the following hierarchy. If an endpoint in the sequence fails to show a statistically significance then no further testing of the subsequent endpoints in the hierarchy will be performed.

1. Between group comparison of mean change, with respect to baseline, in urine leakage in a provocative pad weight test at Week 12;
2. Within Neurotech Vital Compact group estimate of mean change, with respect to baseline, in urine leakage in a provocative pad weight test at Week 12;
3. Between group comparison of mean change, with respect to baseline, in urine leakage in the 24-hour pad weight test at Week 12;
4. Within Neurotech Vital Compact group estimate of mean change, with respect to baseline, in urine leakage in the 24-hour pad weight test at Week 12;
5. Between group comparison of mean change, with respect to baseline, in the number of incontinence episodes/day recorded using a 7-day voiding diary at Week 12;
6. Within Neurotech Vital Compact group estimate of mean change, with respect to baseline, in the number of incontinence episodes/day recorded using a 7-day voiding diary at Week 12;
7. Between group comparison of the mean improvement, with respect to baseline, in Incontinence Quality of Life Questionnaire (I-QOL) score at Week 12;
8. Within Neurotech Vital Compact group estimate of mean improvement, with respect to baseline, in Incontinence Quality of Life Questionnaire (I-QOL) score at Week 12;
9. Between group comparison of mean change, with respect to baseline, in the number of pads used/day recorded using a 7-day voiding diary at Week 12;
10. Within Neurotech Vital Compact group estimate of mean change, with respect to baseline, in the number of pads used/day recorded using a 7-day voiding diary at Week 12;
11. Between group comparison of the proportion of subjects achieving dryness at Week 12 (<1g on the provocative pad weight test).

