2.3.3 KEY SECONDARY ENDPOINTS

The key secondary endpoints listed below will be tested only if the primary efficacy endpoint is met. In order to control the type I error rate, the endpoints will be analyzed hierarchically. If an endpoint in the sequence fails to show statistical significance, then no statistical claims can be made for the subsequent endpoints in the hierarchy and further testing will be performed for exploratory purposes only. The analyses will be based on ITT population and the LOCF method will be used to impute missing data.

1. Between group comparison of mean change, with respect to baseline, in urine leakage in a provocative pad weight test at Week 12;
2. Within Vital Compact group estimate of mean change, with respect to baseline, in urine leakage in a provocative pad weight test at Week 12;

3. Between group comparison of mean change, with respect to baseline, in urine leakage in the 24-hour pad weight test at Week 12;
4. Within Vital Compact group estimate of mean change, with respect to baseline, in urine leakage in the 24-hour pad weigh test at Week 12;
5. Between group comparison of mean change, with respect to baseline, in the number of incontinence episodes/day recorded using a 7-day voiding diary at Week 12;
6. Within Vital Compact group estimate of mean change, with respect to baseline, in the number of incontinence episodes/day recorded using a 7-day voiding diary at Week 12;
7. Between group comparison of the mean improvement, with respect to baseline, in Incontinence Quality of Life Questionnaire (I-QOL) score at Week 12;
8. Within Vital Compact group estimate of mean improvement, with respect to baseline, in Incontinence Quality of Life Questionnaire (I-QOL) score at Week 12;
9. Between group comparison of mean change, with respect to baseline, in the number of pads used/day recorded using a 7-day voiding diary at Week 12;
10. Within Vital Compact group estimate of mean change, with respect to baseline, in the number of pads used/day recorded using a 7-day voiding diary at Week 12;
11. Between group comparison of the proportion of subjects achieving dryness at Week 12 (<1 g on the provocative pad weight test).

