2.3.3.1 ANALYSIS OF BETWEEN-GROUP MEAN CHANGES FOR KEY SECONDARY ENDPOINTS

For the between-group comparisons of mean change (endpoints 1, 3, 5, 7, and 9 in the hierarchy noted above), the key secondary hypothesis is that the mean change from baseline to Week 12 for Vital Compact is not equal to that of itouch Sure Pelvic Floor Exerciser:

$$H_0: \mu_{Vital\ Compact} = \mu_{control}$$

$$H_1: \mu_{Vital\ Compact} \neq \mu_{control}$$

where $\mu_{Neurotech\ Vital\ Compact}$ is the mean change from baseline for the Vital Compact group and $\mu_{control}$ is the mean change from baseline for the itouch Sure Pelvic Floor Exerciser group.

To test this hypothesis, a two-sample t-test will be conducted for each endpoint. The difference between device groups will be summarized using mean change, standard deviation, and a 95% confidence interval of the difference. In the event that data are highly non-normal, non-parametric methods (e.g. rank-sum test) may be employed. Normality will be tested using Shapiro Wilk Test.

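### The nested primary superiority test has no place relative to the key secondary sequence, so error is not controlled over the two together; separately, the sequence can continue after a result that favours itouch

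*Protocol*

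**What the plan says.** **Primary.** Protocol 10.3.3 tests non-inferiority with a 5-point margin ("Using a one-sided 2.5% level significance test"). It then adds: "If the primary non-inferiority endpoint is met, a hierarchically nested test of superiority will be performed". That second test is also at one-sided 2.5%. SAP 2.3.2 and 2.3.2.1 repeat the structure: non-inferiority is claimed if the lower 95% limit is above -5%, superiority if it is above 0%.

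**Key secondaries.** Protocol 10.3.5 and SAP 2.3.3 share the opening condition: "The key secondary endpoints listed below will be tested only if the primary efficacy endpoint is met". Under the protocol each is tested at two-sided 5%, in the order 1 to 11. SAP 2.3.3 gives the reason: "In order to control the type I error rate, the endpoints will be analyzed hierarchically". The protocol stops testing at the first non-significant endpoint; the SAP lets later tests run as exploratory only.

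**Direction.** The protocol synopsis and section 5.2 say these endpoints are analysed for superiority, with labelling in view. Yet the hypothesis for steps 1, 3, 5, 7 and 9 is that the mean change on Vital Compact "is not equal to that of itouch Sure Pelvic Floor Exerciser" (SAP 2.3.3.1). The within-group steps 2, 4, 6, 8 and 10 test a mean change different from zero. Only the hypothesis for step 11 has a direction.

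**The concern.** Neither document defines what it means for the primary efficacy endpoint to be met. Protocol 10.3.3 uses the same verb for non-inferiority, and nothing makes superiority a condition for step 1. The natural reading is therefore that passing non-inferiority opens two branches, primary superiority and key secondary 1, each at full alpha, with no order and no split between them. SAP section 4, which lists changes from the protocol's methods, does not address this.

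The second gap concerns direction. The sequence halts only when a step is not significant. If step 1 were significant in favour of itouch, the written rule would still carry the sequence to step 2, a within-group test with no comparator. Vital Compact could then gain a formally sequenced claim on a measure where it had just been shown worse than the control.

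The trial is described as pivotal for FDA clearance and the key secondaries are meant to support labelling. An ambiguity of this kind should be settled before anyone sees unblinded results.

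**Working it through.** **Inputs from the documents.** Margin 5 points; one-sided 0.025; 52% and 71% response; 87 per group for 90% power, raised to 90 per group (Protocol 10.2, SAP 1.4). **Assumption.** The documents give no correlation between the primary statistic and that of key secondary 1, so a range is shown.

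**1. The plan's own figure.** With pooled variance and mean rate (0.52 + 0.71)/2 = 0.615:

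n = 2 × 0.615 × 0.385 × (1.960 + 1.282)² / (0.19 + 0.05)² = 86.4, so 87 per group. The stated figure is reproduced.

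**2. Chance of passing non-inferiority when the devices are equal.** At 52% in both arms, 90 per group:

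- SE = √(2 × 0.52 × 0.48 / 90) = 0.0745
- margin / SE = 0.05 / 0.0745 = 0.671
- non-inferiority passes when Z1 > 1.960 − 0.671 = 1.289, which has probability 9.9%
- superiority passes when Z1 > 1.960, which has probability 2.5%

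**3. Error over the two branches.** Let Z2 be the statistic for key secondary 1, also with no true difference, signed so that positive favours Vital Compact. A false superiority claim occurs if Z1 > 1.960, or if 1.289 < Z1 ≤ 1.960 and Z2 > 1.960. At correlation 0 this is 0.025 + (0.0988 − 0.025) × 0.025 = 0.0268. From the bivariate normal distribution:

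| Correlation | False superiority claim (one-sided) |
|---|---|
| 0 | 2.7% |
| 0.3 | 2.9% |
| 0.5 | 3.2% |
| 0.7 | 3.4% |

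With 71% in both arms the range is again 2.7% to 3.4%. A simulation of 200,000 trials with assumed lognormal leakage (correlation about 0.45) gave 3.2%, against 2.7% for superiority alone.

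**4. Each chain alone.** Non-inferiority then superiority is valid at one-sided 2.5%. Non-inferiority then steps 1 to 11, stopping at the first failure, is valid at two-sided 5%. The excess arises only when the two are combined.

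**5. The adverse-direction path.** With no true differences, the chance that non-inferiority passes while step 1 is significant for itouch is 0.0988 × 0.025 = 0.25% at correlation 0, 0.05% at 0.3 and under 0.01% at 0.5.

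**6. Price of placing superiority before step 1.** At 71% vs 52%, SE = √((0.71 × 0.29 + 0.52 × 0.48)/90) = 0.0711. Power to pass non-inferiority is Φ(0.24/0.0711 − 1.960) = 92%. Power to pass superiority is Φ(0.19/0.0711 − 1.960) = 76%. Suppose key secondary 1 has 50% power by itself:

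| True rates | Correlation | Success of step 1, non-inferiority gate | Success of step 1, superiority gate |
|---|---|---|---|
| 71% vs 52% | 0.6 | 49% | 46% |
| 71% vs 52% | 0 | 46% | 38% |
| 62% vs 52% | 0.6 | 37% | 22% |

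**The case against.** **The plan never claims control over the combined family.** Its error-control sentence is attached to the eleven key secondaries, and the labelling language refers to those alone. This stands. A reader might infer that the key secondary hierarchy itself fails; the documents do not support that, because non-inferiority followed by 1 to 11 is a valid fixed sequence. What remains is that superiority is also a planned formal claim, tested at full alpha and left outside any stated order.

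**The two-branch reading rests on an undefined phrase.** Also fair: the defect is partly a missing definition. But the alternative reading, that superiority gates the key secondaries, is stated nowhere, and leaving the choice open until after unblinding is itself the problem.

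**A result favouring itouch is not a type I error.** Correct. A reader might infer that continuing past an adverse result inflates the error rate. Against a two-sided null, a significant result for itouch when itouch is truly better is a correct rejection, and passing alpha on afterwards does not inflate error for the nulls as written. The 0.25% at correlation 0 also cannot be added to the 3.4% at correlation 0.7, where the path has almost no probability. The stated superiority purpose in the synopsis and section 5.2 hints at a direction, but the continuation rule does not carry it.

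**The excess is small.** It is under one percentage point, because equal devices pass non-inferiority only about 10% of the time at this sample size.

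**Conclusion.** The point holds in two limited parts.

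- **Combined error.** On the natural reading of the gates, the chance of a false superiority claim over primary superiority and the key secondaries together is about 2.7% to 3.4% one-sided against 2.5%, an excess of 0.2 to 0.9 points. This assumes equal true response of 52%, 90 per group, no true difference on key secondary 1, and correlation between 0 and 0.7. Both endpoints come from the same Week 12 provocative pad test, so a clearly positive correlation, and with it the upper part of the range, is plausible. The rate stays below 5%.
- **Direction.** The rule allows the sequence to continue after a significant result for itouch, contrary to the stated superiority purpose. This is a flaw in how claims are licensed, with no error inflation attached.

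Neither part undermines the non-inferiority conclusion or the key secondary sequence taken by itself. Both merit correction before unblinding.

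**What to change.** Amend SAP 2.3.2 and 2.3.3 before unblinding:

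1. Define the condition for opening the key secondaries as non-inferiority on the primary endpoint.
2. Settle the place of primary superiority by choosing one option:
   - **After step 11.** Key secondary power is unchanged, but the superiority claim then depends on all eleven steps passing.
   - **Before step 1.** All eleven key secondaries then depend on superiority. The gate's power falls from about 92% to 76% at 71% vs 52%, and the loss is larger if the true difference is smaller, as tabulated above. In a trial sized for non-inferiority this is a substantive choice, although the text change is short.
   - **Outside the controlled family.** State that superiority supports no controlled claim. This costs only the strength of that claim.
3. Continue past steps 1, 3, 5, 7 and 9 only if the result is significant in favour of Vital Compact, and past the within-group steps only if it is significant in the direction of improvement. This takes no power from any favourable claim.

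No option needs more patients.

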10.3.6 Hypothesis tests

The key-secondary hypothesis for the between group tests (1, 3, 5, 7 and 9 in the hierarchy listed above) is that the key-secondary endpoints of Neurotech Vital Compact is not equal to the itouch Sure Pelvic Floor Exerciser.

Using a two-sided 5% level significance test:

$$H_0: \mu_{\text{Neurotech Vital Compact}} = \mu_{\text{CONTROL}}$$

$$H_a: \mu_{\text{Neurotech Vital Compact}} \neq \mu_{\text{CONTROL}}$$

Where $\mu_{\text{Neurotech Vital Compact}}$ and μ_{CONTROL} are the mean responses for the key-secondary variable for Neurotech Vital Compact and the itouch Sure Pelvic Floor Exerciser, respectively.

The hypothesis for key-secondary endpoint 11 is as follows, using a one-sided 2.5% level significance test:

$$H_0: p_{\text{Neurotech Vital Compact}} - p_{\text{CONTROL}} \leq 0\%$$

$$H_1: p_{\text{Neurotech Vital Compact}} - p_{\text{CONTROL}} > 0\%$$

Where $p_{\text{Neurotech Vital}}$ is the proportion of patients who become dry on receiving Neurotech Vital Compact and similarly p_{CONTROL} for the iTouch Sure Pelvic Floor Exerciser.

The key-secondary hypothesis for the within-group tests (2, 4, 6, 8 and 10 in the hierarchy listed above) is that the key-secondary endpoints of Neurotech Vital Compact are not equal to 0.

Using a two-sided 5% level significance test:

$$H_0: \mu_{\text{Neurotech Vital Compact}} = 0$$

$$H_a: \mu_{\text{Neurotech Vital Compact}} \neq 0$$

Where $\mu_{\text{Neurotech Vital Compact}}$ is the mean responses for the key-secondary variable for Neurotech Vital Compact.

